### **Statistical Analysis Plan**

**General Analytic Strategies.** The number of participants recruited and retained will be documented, and comparisons will be made on all study variables between those who complete and those who drop out of the study in order to inform external validity. Compliance and intervention dose will be assessed with time-stamped electronic records generated through the app. All data will be inspected for normality and transformations will

be applied as needed. Missing questionnaire data will be handled using multiple imputation if data are missing completely at random (Enders, 2013).

**Specific Aim 1.** There are multiple ways to assess participants' engagement to determine the acceptability of the intervention. The first two involve examining how much adolescents use the mobile application. We will examine compliance during the 3-week intervention period by comparing the amount of application use (as recorded electronically) in the intervention group to the control group. We will also examine use during the follow-up periods (12 weeks), when it is optional. Both of these usage questions can be answered with t-tests comparing use between groups.

The other two ways of measuring acceptability are more direct. Participants will complete a satisfaction questionnaire during the post-assessment, and we will compare scores on these questions between groups using t-tests. Finally, participants in the intervention condition will answer a question after each mindfulness exercise regarding how helpful it was using a 0-100 scale ranging from not at all helpful to extremely helpful. Scores on this question can be averaged and examined separately for each type of mindfulness exercise to see if they fall above the benchmark of 50, indicating that adolescents find them helpful in the moment. With all statistical analyses, we will use best current practices regarding correction for multiple tests.

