**Specific Aim 2.** Testing of the hypothesis that the intervention will reduce symptoms through the mediating effect of reduced rumination will be accomplished by capitalizing on both trait-level questionnaire data and state-level EMA data. Using trait-level data, an indirect effect model will be tested to examine the effect of condition (EMA-only vs. EMA + Mindfulness) on each outcome (depressive symptoms, anxiety symptoms, parent-reported internalizing symptoms, and self-injury) through the indirect effect of rumination (see Figure 2). These analyses will be accomplished using the PROCESS macro (Hayes, 2013) for SPSS (IBM Corp.) which relies on bootstrapping to generate bias corrected confidence intervals. This approach is particularly well-suited for testing mediation models with relatively small sample sizes. It also allows for the addition of covariates and/or moderators if inclusion of them are warranted. For example, if there are sex differences in rumination and/or symptoms, as is likely based on previous research (e.g., Hilt, McLaughlin, & Nolen-Hoeksema, 2010), sex can be covaried or tested as a moderator of effects (**Exploratory Aim**) using methods described by Preacher, Rucker, and Hayes (2007). Dose can also be examined as a covariate, to test whether variability in use of the mobile application affects outcomes. These indirect effects models will be tested at each time period (post, follow-up 1, and follow-up 2). If the hypothesis is supported for

[figure not shown]

Figure 2. Conceptual indirect effect model. Note that moderators (e.g., sex) may also be included.

the post-intervention time period, it will be helpful to see if effects are maintained at 6 and 12 weeks. If the hypothesis is not supported at the post-intervention period, it will be possible to examine delayed effects at the follow-up time points. For example, the intervention could reduce rumination first and have a delayed effect on symptoms.

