The primary hypothesis can also be examined on a finer-grain time scale using state-level EMA data to test whether a mindfulness exercise results in reduced negative mood immediately or at subsequent time points relative to each person's average level of mood. Relatedly, we can examine whether mindfulness exercises reduce state rumination compared to one's average level of state rumination and if so, test mediation. Similar to the trait-level models, covariates (i.e., between-person factors such as sex, SES, and race/ethnicity) may be included if warranted. These multilevel models will be estimated in Mplus (Muthén & Muthén, 1998-2015) using maximum likelihood estimation with robust standard errors to account for the nested nature of the data. This approach will allow for the examination of between- and within-person variation in outcomes and is consistent with current recommendations for handling missing data (Baraldi & Enders, 2010).

Although rumination is the proposed mediator, we can also test an alternative mechanism, i.e., changes in mindfulness (**Exploratory Aim**). Another mindfulness intervention found that changes in state mindfulness predicted changes in trait mindfulness (Kiken, Garland, Bluth, Palsson, & Gaylord, 2015). Furthermore, there appears to be an inverse relationship between trait mindfulness and depressive symptoms (e.g., Way, Creswell, Eisenberger, & Liberman, 2010). Thus, it is possible that the intervention will improve symptoms by increasing mindfulness, reducing rumination, or both. Both trait- and state-level mindfulness can be included as mediators in the above-mentioned models (Preacher & Hayes, 2008).

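### Multiple imputation of questionnaire data is tied to data missing completely at random, and no method is named for questionnaire data missing at random

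*Combined protocol and SAP*

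**What the plan says.** Under General Analytic Strategies, the Statistical Analysis Plan states: "Missing questionnaire data will be handled using multiple imputation if data are missing completely at random". It does not say how MCAR would be judged, what happens if it is rejected, or which variables enter the imputation model. The same paragraph plans a comparison "between those who complete and those who drop out of the study in order to inform external validity", and no choice of method follows from it.

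Specific Aim 2 applies trait-level indirect-effect models to four questionnaire outcomes (depression, anxiety, parent-reported internalizing symptoms, self-injury), with rumination as mediator, at post and at both follow-ups. They are fitted with the PROCESS macro, "which relies on bootstrapping to generate bias corrected confidence intervals". No missing-data method is given for them. On covariates the plan says: "It also allows for the addition of covariates and/or moderators if inclusion of them are warranted". Baseline scores are not committed to.

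The state-level EMA models are multilevel models fitted in Mplus "using maximum likelihood estimation with robust standard errors to account for the nested nature of the data", and the plan links that approach to recommendations on missing data. Aim 2, under Aims of the study and significance, also mentions multilevel modelling of the effect of state changes on trait levels.

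**The concern.** The condition attaches imputation to the case where it is least needed. Under MCAR, imputation is valid and recovers information, for example from skipped items on long scales, but there is no bias to remove. Under MAR, completers can give a biased arm comparison and a correctly specified imputation removes that bias. The rule does not provide for this case.

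Departures from MCAR are plausible on the plan's own terms. The Adverse Event section withdraws participants with serious suicidal concerns until these are resolved, and Assessment of Safety screens for them with the depression and self-injury instruments that also serve as Aim 2 outcomes. Any later data lost in this way would depend on observed scores. The documents give no frequency, and it may be small.

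Two things are at stake: possible bias in the arm effects and the mediated effect, and an analysis choice left open until the data are known.

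**Working it through.** The plan states no dropout rate, standard deviation, effect size or power, so there is no figure to reproduce. The only design inputs are 150 participants at 1:1, so 150/2 = 75 per arm (Sample). Everything else below is assumed and illustrative: continuous scores (so not necessarily self-injury), and completers analysed when nothing is imputed.

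**1. When does imputation remove bias?** 75 per arm, true difference -0.40 SD, baseline-outcome correlation 0.6, 1,500 simulated trials per row, dropout of 10/20/30%.

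| Missingness | Completers, unadjusted | Completers, baseline-adjusted | Multiple imputation by arm from baseline |
|---|---|---|---|
| MCAR | -0.402/-0.396/-0.396 | -0.401/-0.392/-0.394 | -0.401/-0.395/-0.397 |
| Depends on baseline, same in both arms | -0.394/-0.406/-0.398 | -0.395/-0.402/-0.398 | -0.394/-0.405/-0.398 |
| Depends on baseline in app arm only (equal rates) | -0.479/-0.548/-0.609 | -0.396/-0.397/-0.398 | -0.398/-0.398/-0.398 |

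Under MCAR completers are unbiased, and imputation changes only precision (empirical SD 0.187 against 0.196 at 30%). In the last row the unadjusted bias is 0.609 - 0.40 = 0.21 SD at 30%, and either imputation or a baseline covariate removes it.

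**2. A MAR case that a baseline covariate does not cure.** Let follow-up dropout depend on the observed post score, logit P(dropout) = a + s × post, with a set to give the stated rate. True effect zero, adjacent-wave correlation 0.6 to 0.7, baseline to follow-up 0.5 to 0.6, 2,000,000 simulated participants per arm, baseline covariate included.

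| Dropout (app vs control), slope s per SD | Spurious arm difference (SD) |
|---|---|
| 10% vs none, s = 1.0 | -0.03 |
| 20% vs none, s = 1.0 | -0.05 |
| 30% vs none, s = 1.0 | -0.07 to -0.08 |
| 20% vs none, s = 0.5 to 1.5 | -0.03 to -0.07 |
| 20% vs 20%, s = 1.0 in both | 0.00 |
| 20% vs 15%, s = 1.0 in both | -0.01 |
| 20% vs 20%, s = 1.0 vs 0.5 | -0.02 |
| 20% vs 15%, s = 1.0 vs 0.5 | -0.03 |

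Where dropout is in the app arm only, imputing from baseline and post returns values within 0.001 of zero.

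**3. Size against sampling error.** SE = √[(1 - r²)(1/n₁ + 1/n₂)], where r is the baseline to follow-up correlation.
- No dropout, r = 0.6: √[0.64 × (1/75 + 1/75)] = 0.13.
- 20% in both arms (60 each), r = 0.5: √[0.75 × (1/60 + 1/60)] = 0.16.

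Two-sided rejection at a nominal 5% is Φ(-1.96 + |bias|/SE) + Φ(-1.96 - |bias|/SE).
- 20% vs 15%, slopes 1.0 vs 0.5, r = 0.6: SE = √[0.64 × (1/60 + 1/63.75)] = 0.144; 0.03/0.144 = 0.21; rejection about 5.5%.
- 20% in one arm, bias -0.054: 6.5% to 6.8%.
- 30% in one arm, bias -0.077: about 8%.

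**4. Indirect effect.** 10,000 trials of 75 per arm, rumination-symptom correlation 0.5, dropout driven by baseline rumination (s = 1.0), bias-corrected bootstrap interval, true indirect effect zero. Rejection is 7% with no dropout and 7% with identical 20% dropout. It is 12% to 13% with 20% dropout in one arm and no covariate, and 7% to 8% once a baseline covariate is added. In a separate run of 4,000 trials, full-information maximum likelihood with baseline as auxiliary gave about 7%.

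**5. What the imputation model must contain.** Adolescents report the mediator and parents report one outcome, so either can be missing without the other. With a true rumination-symptom slope of 0.50 and baseline correlation 0.6, imputing the mediator without the concurrent outcome gives 0.47, 0.44 and 0.40 at 10%, 20% and 30% missing. Including the outcome gives 0.50.

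**The case against.** The best defence is that the sentence says *if*, not *only if*. The plan is silent on MAR data and does not forbid imputing them, and imputation under MCAR is legitimate. That stands: a reader might infer a commitment to analyse completers whenever MCAR fails, and the documents do not support this. The completer analysis above is an assumption. The wording may also be a slip for missing at random, in which case the correction is the same.

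A reader might also infer that maximum likelihood never reaches trait data. That is too strong, because the modelling of state changes on trait levels may bring some in. The PROCESS models still remain uncovered.

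Finally, the bias is small against sampling error, and its larger values need dropout in one arm alone. The plan describes the same app platform, reminders, bonus and questionnaires without distinguishing arms; the arms differ in the exercises. This stands and limits the severity. It does not close the gap, because the choice of method stays open whatever the bias.

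**Conclusion.** The point holds, at minor to moderate severity. The only stated rule for missing questionnaires carries the wrong condition, and the trait-level mediation models have no named method under MAR.

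The documents do not show that results will be biased: they give no dropout rate and no sign that dropout depends on arm. With a baseline covariate and the assumed correlations and slopes, bias runs from zero (dropout alike in both arms) through about -0.03 SD (modestly different) to about -0.08 SD (30% in one arm only), against a standard error of 0.13 to 0.16 SD.

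The 12% to 13% false-positive rate should not be read as the expected consequence. It needs both one-arm dropout and no baseline covariate, and about 7% arises with no missing data at all.

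**What to change.** Replace the sentence with text such as: *Missing questionnaire data will be handled under a missing-at-random assumption by multiple imputation or full-information maximum likelihood, regardless of any MCAR test. The imputation or likelihood model will include arm, baseline and all other available waves of the outcome and the mediator, the concurrent outcome when the mediator is missing and the concurrent mediator when the outcome is missing, and logged app use as an auxiliary variable.*

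State how this combines with the bootstrap: either impute within each bootstrap sample, or fit the mediation model by full-information maximum likelihood in Mplus, which the plan already names for the EMA models. The imputation model should suit the scale of the self-injury outcome. A delta-adjusted sensitivity analysis for data missing not at random is optional.

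The cost is a few sentences and modest extra programming, with no new data. If Mplus is chosen, it replaces PROCESS for these models.

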## Overview

The primary objective of this study is to examine whether the mindfulness mobile application engages adolescents and reduces rumination and subsequent psychopathology. We hypothesized that adolescents in the mindfulness intervention condition would experience a reduction in symptoms of depression, anxiety, and self-injury relative to those in the control group and that this would be accounted for by a reduction in the tendency to ruminate. We test this by using a randomized, controlled design, comparing the intervention group to a control group that uses the same mobile application for EMA but does not receive the mindfulness exercises.

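### The SAP names no between-arm comparison of any symptom score: whether the app reduces symptoms relative to control is addressed only through indirect-effect models, whose rumination-to-symptom path is not randomised.

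*Combined protocol and SAP*

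**What the plan says.** The Overview makes two claims. The first is that adolescents given the mindfulness exercises will "experience a reduction in symptoms of depression, anxiety, and self-injury relative to those in the control group". The second is that a reduced tendency to ruminate explains this. The first is a statement about the difference between randomised arms; the second is about mechanism.

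The SAP then sets out the following.

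- **Specific Aim 1** compares arms on app use ("Both of these usage questions can be answered with t-tests comparing use between groups") and, also by t-test, on satisfaction. No symptom score is compared.
- **Specific Aim 2, trait level**, opens with "Testing of the hypothesis that the intervention will reduce symptoms through the mediating effect of reduced rumination" and specifies that "an indirect effect model will be tested to examine the effect of condition (EMA-only vs. EMA + Mindfulness) on each outcome", by way of rumination. The outcomes are depressive symptoms, anxiety symptoms, parent-reported internalizing symptoms and self-injury, each at post, follow-up 1 and follow-up 2. Inference is by bias-corrected bootstrap intervals. Covariates are optional, and baseline scores are not named among them.
- **Specific Aim 2, state level**, asks whether an exercise "results in reduced negative mood immediately or at subsequent time points relative to each person's average level of mood", and treats state rumination in the same way.
- **Exploratory aim**: mindfulness is added as an alternative mediator.

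On multiplicity the SAP says "With all statistical analyses, we will use best current practices regarding correction for multiple tests", without naming a method or a family. The Aims section also describes Aim 1 as the efficacy test, whereas Aim 1 as listed there and in the SAP is acceptability and engagement.

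**The concern.** Randomisation protects the comparison of arms on rumination and the comparison of arms on symptoms. It does not protect the association between rumination and symptoms, because trait rumination is a questionnaire score and not an assigned condition. Anything that raises both will produce that association. An indirect effect multiplies the protected path by the unprotected one, which allows two errors if it is read as evidence of benefit:

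- it can exclude zero when the arms do not differ on symptoms;
- it can miss a benefit that does not run through rumination. The SAP itself allows for other routes: "it is possible that the intervention will improve symptoms by increasing mindfulness, reducing rumination, or both".

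The Aims section holds out a larger trial if the app shows efficacy, but no result is designated to show it. Whether the arm difference is reported, and how much weight it carries, is left to be settled after the data are seen.

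**Working it through.** **Step 1: match each planned analysis to the between-arm hypothesis in the Overview.**

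| Planned analysis | Contrast | Tests arm difference in symptoms? |
|---|---|---|
| t-tests, Aim 1 | arms, on use and satisfaction | No |
| Indirect effects via rumination (4 outcomes x 3 times = 12) | arm to rumination to symptom | No, product of paths |
| EMA multilevel models | person against own average, momentary mood and state rumination | No |
| Exploratory mindfulness mediation | arm to mindfulness to symptom | No, product of paths |

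**Step 2: is the arm difference obtainable?** For a linear outcome with the same cases and covariates, total = direct + indirect (c = c' + ab), so the planned fits contain it. This need not hold for a non-linear self-injury model.

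**Step 3: how far can the two answers diverge?** The documents give about 75 per arm, but no effect size, SD, alpha or correlation. All of these are assumed here: two-sided 0.05, residual SD 1, no baseline adjustment (none is specified), and correlation rho = 0.3 to 0.5 between rumination and symptoms arising from shared causes only.

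Model: M = -a·X + e1; Y = -d·X + rho·e1 + sqrt(1 - rho²)·e2, where X is arm, M rumination and Y symptoms.

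*No symptom effect (d = 0), rumination falls by a = 0.3.* Substituting e1 = M + a·X gives b = rho and c' = +a·rho. The indirect effect is -0.3 x 0.3 = -0.09 to -0.3 x 0.5 = -0.15, the direct effect is +0.09 to +0.15, and the total is exactly 0.

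Hand check, requiring both paths to be significant:
- SE(a) = sqrt(2/75) = 0.163; z = 0.3/0.163 = 1.84; power 45%.
- SE(b) = sqrt((1 - rho²)/147) = 0.079 (rho 0.3) or 0.071 (rho 0.5); z = 3.8 or 7.0; power 97% or about 100%.
- Product: about 44-45%.

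Simulation with the bias-corrected bootstrap that the SAP names (2,000 trials per setting, 5,000 draws each), counting intervals wholly on the side favouring the app:

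| Truth | Indirect, uncorrected | Indirect, Bonferroni over 12 | Arm test, uncorrected |
|---|---|---|---|
| Rumination -0.3 SD, symptoms 0 | about 50% | about 17-21% | about 5-6% |
| Rumination -0.5 SD, symptoms 0 | about 88% | about 54-61% | about 5% |
| Rumination 0, symptoms -0.5 SD | about 3-5% | under 1% | about 86% |

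The Bonferroni range in the first row covers separate runs. Bonferroni over 12 is itself an assumption, since the SAP names no method. A smaller independent re-run (1,000 trials, 2,000 draws) gave 48-50%, 87-89% and 2-4% for the uncorrected indirect column.

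**Step 4: effect of baseline adjustment.** Adjusting for baseline lowers the residual SD, but it can also remove much of any stable shared cause. With residual SD 0.7 and residual correlation 0.1, the 0.3 SD scenario gives about 24%. The rates in Step 3 therefore apply to unadjusted models only.

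**Step 5: what the arm test can detect.** At 80% power: (1.96 + 0.84) x sqrt(2/75) = 0.46 SD, unadjusted and uncorrected. The 95% CI half-width is 1.96 x sqrt(2/75) = 0.32 SD.

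**The case against.** **Mediation software can estimate the total effect.** This stands for linear outcomes. A reader might infer that the trial cannot show whether symptoms differ by arm; the documents do not support that. The gap is that the estimate is neither named nor given a role.

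**The hypothesis judged in Specific Aim 2 is mediation.** This also stands. When the SAP says "If the hypothesis is not supported at the post-intervention period, it will be possible to examine delayed effects at the follow-up time points", the hypothesis meant is the one that opens that section. A reader might infer that the plan will declare efficacy from an indirect interval, but no sentence says so. The narrower risk is that nothing else is named as evidence on symptoms.

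**The EMA models bear on benefit.** In part. Exercises are assigned by chance within the app, with odds that depend on rated mood, and the models cover variation between as well as within persons. An exercise-to-mood contrast that respects that rule would be informative about momentary mood. It is still not an arm comparison on a symptom scale.

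**Baseline adjustment would shrink the problem.** Probably, as Step 4 shows. A reader might infer that a smaller residual SD makes the false-positive rate higher still; that would require the shared-cause correlation to survive adjustment unchanged. However, the SAP does not name baseline adjustment.

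**Figure 2 may draw a direct path.** It is not shown. Its caption describes an indirect effect model, and a drawn path would not be a prioritised test.

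**This is a proof of concept.** That excuses modest power. It does not explain why the first half of the stated hypothesis has no named test.

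**Conclusion.** The concern holds in this form: the SAP names no between-arm effect on any symptom scale, and the only arm-based symptom analyses are indirect effects whose second path is not randomised. That conclusion rests on the text and not on the simulated rates.

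The rates show what is possible. With 75 per arm, unadjusted models and a shared-cause correlation of 0.3 to 0.5, the indirect interval can favour the app in about half of trials (0.3 SD fall in rumination) or nearly nine in ten (0.5 SD) when symptoms do not change. It can almost always miss a 0.5 SD benefit by another route. The rates fall sharply if adjustment removes most of the shared cause, and the documents give no basis for saying which inputs are likely.

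This should be fixed before analysis. Because the quantity is largely recoverable and the study is early-stage, it is a gap in specification and priority and does not invalidate the design.

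**What to change.** In Specific Aim 2, ahead of the mediation models:

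1. Add the baseline-adjusted difference between arms, with 95% CI, for each of the four symptom outcomes and for trait rumination, in all randomised participants as assigned, at post and both follow-ups. Use a model suited to the scale for self-injury.
2. Have the sponsor name one symptom outcome and one time point as the main efficacy comparison, so that 12 unranked mediation tests are not simply joined by 12 unranked arm tests. State the family and method for the promised multiplicity correction.
3. Adjust the indirect-effect models for baseline rumination and the baseline of the outcome. Keep them as the mechanism analysis, and state that they do not by themselves show efficacy.
4. In the Aims section, reconcile the description of Aim 1 as efficacy with Aim 1 as listed (acceptability and engagement).

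The cost is a few sentences and a small analysis of data already planned. The drawback is that where the app does lower rumination, the arm test is less likely to be significant than the indirect effect, with 80% power only for about 0.46 SD unadjusted and uncorrected. Baseline adjustment would improve this: if it reduced the residual SD to 0.7, the figure would be 0.7 x 0.46 = 0.32 SD.

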Rumination has been identified as a transdiagnostic risk factor involved in the development of several forms of psychopathology including depression, anxiety and self-injurious behavior (for reviews see Aldao, Nolen-Hoeksema, & Schweizer, 2010; Nolen-Hoeksema & Watkins, 2011; Nolen-Hoeksema, Wisco, & Lyubomirsky, 2008). Rumination involves repetitively focusing on one's negative emotions and brooding about their meaning and consequences (Nolen-Hoeksema, 1991). A meta-analysis showed that rumination is associated with depressive symptoms, concurrently and prospectively among adolescents (Rood, Roelofs, Bogels, Nolen-Hoeksema, & Schouten, 2009), and rumination also prospectively predicts depression diagnosis among adolescents (Abela & Hankin, 2011). Studies have also found that rumination concurrently and prospectively predicts anxiety symptoms in adolescents (e.g., McLaughlin & Nolen-Hoeksema, 2011; Muris, Roelofs, Meesters, & Boomsma, 2004). Finally, rumination has emerged as an important risk factor for both nonsuicidal self-injury (e.g., Hilt, Cha, & Nolen-Hoeksema, 2008; Barrocas, Gilleta, Hankin, Prinstein, & Abela, 2015) and suicidal ideation (e.g., Miranda & Nolen-Hoeksema, 2007; Smith, Alloy, & Abramson, 2006). Given the involvement of rumination in the development of internalizing symptoms and self-injurious behavior, it is an important target for preventive interventions.

Mindfulness meditation is an intervention strategy that has shown promise in targeting rumination. It involves focusing attention on the present moment without judgement (Kabat-Zinn, 2003). Rumination typically involves a perseverative focus on past events (Nolen-Hoeksema et al., 2008), and mindfulness may help alleviate rumination through its focus on the present and emphasis on detaching from mental events, rather than becoming caught up in them as one does while ruminating (Ma & Teasdale, 2004). Trait (i.e., habitual) levels of mindfulness are negatively associated with trait levels of uncontrollable rumination (Raes & Williams, 2010), suggesting these strategies may be antithetical. Indeed, mindfulness meditation interventions have resulted in decreases in distress and negative affect, and decreased rumination appears to be a mediator of these effects (Chiesa & Serretti, 2009).

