### **Sample**

We will recruit 150 adolescent girls and boys, ages 12-15. This age range was chosen to capture the developmental period directly preceding increased rates of depression (Hankin et al., 1998), providing an opportune window for prevention. Participants will be recruited through a recruitment letter mailed to students enrolled in grades 7-10 at a large, local, public school district with over 5000 students in our target age range. In order to maximize the potential of targeting the proposed mechanism, we will only enroll adolescents who report at least moderate baseline levels of trait rumination. This will be accomplished through a 2-question phone screen. Once parents verbally consent and the child has verbally assented, we will ask them to respond to two questions from the Children's Response Style Questionnaire (CRSQ; Abela, Brozina, & Haigh, 2002) that assess brooding, a particularly maladaptive aspect of rumination (Treynor, Gozalez, & Nolen-Hoeksema, 2003). The aggregate of these two questions are highly correlated with the full rumination subscale from the CRSQ ( $r = .79$ ,  $p < .01$ ) and have been associated with depressive symptoms and NSSI in previous work by the PI (Hilt et al., 2008). Adolescents who meet the screening criteria (age 12-15, score of 2 or higher on the brooding questions, and physically and cognitively able to use a mobile application) will be invited to participate in the study. Once they provide written consent and assent, they will be randomly assigned to a condition: EMA only or EMA + Mindfulness at a 1:1 ratio (i.e., ~ 75 participants per condition).

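### Used at a nominal 95% level, the planned bias-corrected bootstrap intervals reject a true null indirect effect about 6% to 8% of the time when one path is zero and the other is moderate or large

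*Combined protocol and SAP*

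**What the plan says.** Under Specific Aim 2, the SAP tests the effect of condition "on each outcome (depressive symptoms, anxiety symptoms, parent-reported internalizing symptoms, and self-injury) through the indirect effect of rumination". The models are run at post, follow-up 1 and follow-up 2, which makes 4 × 3 = 12 trait-level indirect effects. Inference comes from the PROCESS macro, "which relies on bootstrapping to generate bias corrected confidence intervals". The next sentence gives the reason: "This approach is particularly well-suited for testing mediation models with relatively small sample sizes".

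The Sample section sets the size: "We will recruit 150 adolescent girls and boys, ages 12-15", randomised "at a 1:1 ratio (i.e., ~ 75 participants per condition".

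The documents state no confidence level, alpha, number of resamples, path size or dropout rate for these tests. The SAP makes a general promise to correct for multiple tests but names no method.

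**The concern.** An indirect effect is the product of two slopes: condition to rumination (a) and rumination to symptoms (b). It is zero if either slope is zero. The null that matters most here is a = 0 with b not zero: the app leaves rumination unchanged, while rumination still predicts symptoms. The protocol's own Background makes this null realistic, since it reports that "rumination is associated with depressive symptoms, concurrently and prospectively among adolescents".

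In that situation the bias correction tends to move both interval limits away from zero, so the interval excludes zero more often than its nominal level implies. Sections on Aims 1 and 2 specify no separate trait-level test of condition on symptoms, so the trait-level claim of benefit through reduced rumination would rest on these intervals.

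**Working it through.** The documents give no error rate for this test, so there is no figure to reproduce. The check is a simulation.

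**Inputs from the documents:** N = 150, allocated 1:1 (Sample); bias-corrected bootstrap (SAP, Specific Aim 2); condition as X, rumination as M, symptom score as Y (SAP, Specific Aim 2).

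**Assumptions:** nominal 95%, two-sided; 1,000 resamples, with 5,000 as a check; b from 0 to 0.8 and a from 0 to 0.8 SD; no dropout, or 20% dropout (N = 120).

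**Model:** M = aX + e and Y = bM + e, with errors of SD 1. The estimate is the product of the two least-squares slopes. On this scale a slope of 0.2 is a correlation of 0.2/√1.04 = 0.20, and 0.8 is 0.8/√1.64 = 0.62.

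**Intervals:** let z0 = Φ⁻¹(share of bootstrap products below the sample product). The bias-corrected limits are the bootstrap percentiles at Φ(2·z0 ± 1.96). The percentile limits are the same with z0 = 0. The sampling distribution of a product is skewed away from zero, so z0 usually takes the sign of the estimate and both limits move away from zero.

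**Precision:** 10,000 trials per setting. At a 7% rate the simulation error is √(0.07 × 0.93 / 10,000) = 0.26 points.

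Rejection of a true null, N = 150:

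| Setting | Bias-corrected | Percentile |
|---|---|---|
| a = 0, b = 0 | 0.7% | 0.2% |
| a = 0, b = 0.1 | 2.4% | 0.9% |
| a = 0, b = 0.14 | 3.8% | 1.6% |
| a = 0, b = 0.2 | 5.7% | 2.7% |
| a = 0, b = 0.26 | 7.6% | 4.3% |
| a = 0, b = 0.3 | 7.4% | 4.6% |
| a = 0, b = 0.39 | 7.4% | 5.3% |
| a = 0, b = 0.5 | 6.7% | 5.2% |
| a = 0, b = 0.8 | 6.3% | 5.8% |
| b = 0, a = 0.2 | 2.3% | 0.8% |
| b = 0, a = 0.3 | 4.2% | 1.8% |
| b = 0, a = 0.4 | 6.7% | 3.5% |
| b = 0, a = 0.5 | 7.7% | 4.5% |
| b = 0, a = 0.8 | 7.4% | 5.6% |

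**Sensitivity:**
- N = 120, a = 0: bias-corrected 5.0%, 7.5%, 8.1%, 7.1% and 5.6% at b = 0.2, 0.3, 0.39, 0.5 and 0.8.
- 5,000 resamples (5,000 trials), N = 150, a = 0: bias-corrected 6.5%, 7.7% and 7.1% at b = 0.2, 0.3 and 0.5; percentile 3.3%, 5.2% and 5.9%.
- Skewed outcome, N = 150, a = 0: bias-corrected 7.5% and 6.5% at b = 0.3 and 0.5; percentile 5.1% and 5.3%.

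**Width and coverage:** mean bias-corrected width divided by percentile width is 1.00 to 1.07. With a true indirect effect (a = 0.2 to 0.5, b = 0.3 to 0.5), bias-corrected coverage is 93.4% to 95.5%.

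**Tighter thresholds:** if the multiplicity correction were Bonferroni over four tests (5%/4 = 1.25%; an assumption), bias-corrected intervals reject 2.1% to 2.3% at a = 0 and b = 0.3 to 0.5, and percentile intervals 1.3% to 1.4%. Over twelve tests (5%/12 = 0.42%) the figures are 0.77% to 0.83% and 0.37% to 0.47%. With simulation error of about 0.16 points, this last pair shows direction more than size.

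**Power, N = 150, bias-corrected to percentile:**
- a = 0.2: 27.9% to 21.0% (b = 0.3); 27.2% to 23.5% (b = 0.5).
- a = 0.35: 61.9% to 53.3% (b = 0.3); 61.0% to 57.3% (b = 0.5).
- a = 0.5: 86.2% to 80.3% (b = 0.3); 88.8% to 86.9% (b = 0.5).
- Three other settings: 75% to 70%, 81% to 75%, 85% to 83%.

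**The case against.** The strongest reply is that the error rate depends on path sizes that nobody knows. When the non-zero path is small, or both are zero, bias-corrected intervals are conservative. One outcome is parent-reported while rumination is self-reported, so its slope could well be small. This stands, and it limits the point to outcomes that rumination predicts at least moderately.

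The excess is also modest: about 1 to 3 points per test, shrinking at large slopes (6.3% against 5.8% at b = 0.8). Percentile intervals are not exactly on level either; they run from 0.2% to about 6%. Both remarks are fair. The choice is partly a trade of power against error, in a study that describes itself as a proof of concept.

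A third reply is that the small-sample sentence may refer to the macro and bootstrapping in general, not to the bias correction. That reading is plausible. Even so, the sentence does not justify choosing the bias-corrected interval over the percentile one.

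The promise to correct for multiple tests does not answer the point, because the bias-corrected interval stays above its nominal level at tighter thresholds too.

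A reader might infer three stronger claims that the documents and figures do not support:
- *All twelve tests exceed 5%.* The table shows rates well below 5% in part of the plausible range. No familywise rate is claimed either, since the four outcomes at each time point share one condition-to-rumination path and the tests are dependent.
- *The intervals are too narrow.* They are as wide as percentile intervals or slightly wider.
- *These intervals are the only test of the main hypothesis.* The SAP also plans multilevel models of the momentary (EMA) data, including mediation.

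**Conclusion.** The point holds in conditional form. At N = 150 and a nominal 95% level, bias-corrected intervals reject a true null indirect effect about 6% to 8% of the time when exactly one path is zero and the other is moderate or large: b of about 0.2 or more with a = 0, or a of about 0.4 SD or more with b = 0. Outside that region the rate is under 1% to about 4%. Percentile intervals stay at about 6% or below throughout.

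The 95% level is an assumption, so the plan cannot be said to breach a stated 5% error rate. Path sizes, dropout and resample count are also assumed, with the ranges shown. This is a modest, cheaply corrected defect in error control. It does not invalidate the mediation analysis, and coverage is near nominal when a true indirect effect exists.

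**What to change.** In Specific Aim 2 of the SAP, replace the bias-corrected intervals with percentile bootstrap confidence intervals for all trait-level indirect effects. State the confidence level and the number of resamples (for example 10,000). Do not cite small-sample suitability as a reason for the bias-corrected interval. If bias correction is kept, justify it and acknowledge the error rate above.

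The change is one software option. Its cost is nominal power: 6 points or fewer in seven of the nine settings checked (for example 75% to 70%), and 8.6 points in the worst (61.9% to 53.3%). Part of that power came from the inflated error rate, so the real loss is smaller.
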